### 3.2 Population

Participants at least 18 years of age, both healthy controls and those with suspected NAFLD.

**3.4 Sample size:** 30 healthy controls and 70 subjects with biopsy-proven NAFLD

### 3.5 Type of trial

Single-center, phase 1 exploratory study to evaluate the acute (baseline and dynamic) changes in metabolic, energy homeostatic and MR biomarkers in volunteers and patients with biopsy-proven NAFLD measures following IV challenge and dietary fructose restriction.

### 3.6 Outcome measures

#### *Acute Fructose Challenge and MR Biomarkers*

**Primary:** The difference(s) in rate and extent of the dynamic changes in metabolism and energy and water homeostasis in patients with biopsy-proven NAFLD. Liver histology will be the primary predictor of disease and the primary outcome variable to which secondary measures (i.e. MR-biomarkers, metabolic parameters etc) will be measured.

## 4. MRI Biomarkers of NAFLD

### 4.1 MR-based Measures of Hepatic Energy Homeostasis

**$^{31}\text{P}$  Ultra-short TE MRS** pulse sequence used in the Duke Center for Advanced MR Development (CAMRD) for the dynamic measurement of phosphorus metabolites is very similar in design to the UTE-MRS method by Cortez-Pinto, et al. (24) just without the localization gradients. With a hard pulse excite of 100  $\mu\text{s}$ , we can acquire an FID signal as short as 70  $\mu\text{s}$  from the hard pulse center as compared with a nominal echo time of 2 ms for the standard Siemens slice-select excitation sequence. This gives 2-3 times the SNR for the short  $\text{T}_2$  metabolites in the  $^{31}\text{P}$  spectrum.

All study scans will be taken on a 3T Siemens TIM Trio-CT scanner in CAMRD. We will contract with Clinical MR Solutions ([name], Brookfield, WI) to set the specifications for a transmit/receive (TX/RX) Helmholtz-style  $^{31}\text{P}$  tuned flex-coil to provide superior B1 homogeneity to our current surface coil design. Raw data will be transferred off scanner and analyzed using a suite of MRS processing and fitting software written by [name].

Possible Problems and Alternative Strategies – If data quality of the UTE MRS is insufficient to characterize the signal changes observed in volunteers and patients, then we will investigate the use of a single dimension encoding method to attempt to exclude confounding signals from tissues surrounding the liver. If problems arise with the data processing and analysis, the jMRUI program can also be used. An additional small reference phantom mounted on the  $^{31}\text{P}$  coil will identify its spatial location on MRI.

## 5. Intravenous Fructose Challenge with MRS Measures of Energy Homeostasis

IV fructose challenge with MRS measures of energy homeostasis will be performed in the morning after an overnight fast. For all subjects, a vein will be catheterized and a venous blood sample drawn for laboratory evaluation (uric acid, glucose, insulin, lipids, and free fatty acids). A slow infusion of isotonic sodium chloride solution will be started to maintain catheter patency. After baseline MR data sets are obtained, fructose (250 mg/kg of body weight) dissolved in 25 to 50 mL of isotonic sodium chloride solution will be infused rapidly (over 30-60 seconds) through the indwelling venous catheter; further spectra will be collected for 1 hour. The slow saline infusion will be continued until the end of the study. At that time, another venous blood sample will be collected for laboratory evaluation (uric acid, glucose, insulin, lipids, and free fatty acids).

## 6. Standardized Life-Style and Dietary Research Questionnaires

**6.1 Alcohol Use Disorders Identification Test (AUDIT)** is a 10-item questionnaire with a simple scoring scale that will be administered during screening visit 1. A 3- item interim drinking history (AUDIT-C) measuring consumption in the past 90 days will be obtained during follow-up visits at 3 and 6 months

**6.2 Health Related Quality of Life (HRQOL; SF-36)** is a 36-item, self-report measure designed to assess the quality of life in patients that will be administered during screening.

**6.3 Automated Self-Administered 24 Hour Recall (ASA24™)** is a 24 hour dietary recall tool which will be utilized for the purpose of assessing average fructose consumption. The National Cancer Institute ASA24™ is web-based, allowing patients to access the web-site at their convenience. It has long been regarded as the best methodology to measure food intakes for dietary surveillance, nutritional epidemiology, clinical research, and intervention research because it provides the highest-quality and least biased dietary data for a single day. This method allows collection of detailed intake and portion sizes, and because the data collection occurs after the consumption, this methodology does not affect what an individual chooses to eat on a given day. The close proximity in time to the intake day minimizes memory and cognitive issues that afflict other methodologies. ASA24™ has been developed to permit unannounced, automated, and self-administered 24HR, enabling the administration of multiple days of recalls in large-scale

epidemiologic studies, surveillance studies, behavioral trials, or clinical research, thus enhancing researchers' ability to assess usual dietary intakes. The format and design of ASA24™ are based on a modified version of the interviewer-administered Automated Multiple Pass Method (AMPM) 24HR developed by the U.S. Department of Agriculture (USDA). ASA24™ consists of a respondent Web site and a Researcher Web site. The Respondent Web site allows study participants to report their intake for the previous day. The Researcher Web site allows researchers to register a study and its participants, set study parameters (e.g., number of recalls, number of attempts per recall, time to complete a recall), manage study logistics, and obtain analysis files. The investigators and study coordinators will review this instruction document completely and also to become familiar with the Respondent Web site in order to effectively and successfully use ASA24™. An overview of the Respondent Web site is available online at <http://riskfactor.cancer.gov/tools/instruments/asa24/info.html>. The ASA24™ allows for scheduled and non-scheduled responder recall nutritional data collection, would accommodate the number of patients in the proposed study, will allow for detailed analysis of nutritional data, and is free tool to researchers.

**6.4 NCI Dietary Health Questionnaire (DHQ\*Web)** is a web-based version identical in content to the original DHQ. By automating the DHQ and providing it on the Web for public use, researchers have another tool to collect and analyze food frequency questionnaire data. DHQ\*Web takes advantage of what automated and electronic questionnaires are able to do -- respondents follow automated skip patterns, are queried to complete all questions before proceeding to the next, navigate within the instrument to correct or modify responses, and can log in at any time to complete the questionnaire, starting where they left off. DHQ\*Web provides efficiency with respect to data quality because respondents cannot complete the questionnaire with missing or inconsistent responses. Patient will be asked to complete the DHQ at entry.. An overview of the respondent web site is available online at <http://riskfactor.cancer.gov/DHQ/webquest/index.html>.

## 7. Liver Histology

Liver histology is the “gold standard” by which to define disease severity for NAFLD. MRI biomarkers as well as the metabolic and energy homeostatic measures associated with histologic features of NAFLD.

## 8. Patient Selection

**8.1 Recruitment:** Thirty healthy controls and 70 patients with NAFLD will be recruited from the Duke Liver Clinics. Eligible patients will be identified and recruited by the principle investigator and/or sub-investigator. Recruitment into the study will be performed without regard to gender or ethnicity as any patient with suspected NAFLD will be considered eligible if all inclusion and no exclusion criteria are met.

### 8.2 Inclusion criteria

Patients must satisfy all of the following criteria to be eligible for enrollment:

- Age > 18 years as of the initial screening interview and provision of consent
- Healthy control as defined by normal liver aminotransferases AND no evidence of NAFLD on radiologic imaging studies OR liver biopsy (if one had been historically performed for evaluation of suspected liver disease).

OR

- Patients who have had a liver biopsy showing NAFLD within 6 months of the Screening visit or patients who will be undergoing a standard of care percutaneous liver biopsy for NAFLD will be consented. Additionally, anyone with a prior diagnosis of NAFLD or NASH-related cirrhosis (histologically or clinically) may also enroll without having had a recent historical biopsy.

### 8.3 Exclusion criteria

Patients who satisfy any of the following exclusion criteria will be ineligible for enrollment:

- Current or history of significant alcohol consumption for a period of more than 3 consecutive months within 1 year prior to screening (significant alcohol consumption is defined as more than 20 g/day in females and more than 30 g/day in males, on average)
- Inability to reliably quantify alcohol consumption based upon local study physician judgment
- Prior or planned (during the study period) bariatric surgery
- Uncontrolled diabetes defined as HbA1c 9.5% or higher within 60 days prior to enrollment
- A platelet count below 90,000/mm^3
- Clinical evidence of hepatic decompensation as defined by the presence of any of the following abnormalities:
  - Serum albumin less than 3.2 g/dL
  - INR greater than 1.3
  - Direct bilirubin greater than 2.0 mg/dL
  - History of esophageal varices, ascites or hepatic encephalopathy
- Evidence of other forms of chronic liver disease (with the exception of a prior diagnosis of NAFLD or NASH-related cirrhosis)
  - Hepatitis B as defined by presence of hepatitis B surface antigen (HBsAg)
  - Hepatitis C as defined by presence of hepatitis C virus (HCV) RNA or positive hepatitis C antibody (anti-HCV)
  - Evidence of ongoing autoimmune liver disease as defined by consistent liver histology
  - Primary biliary cirrhosis as defined by the presence of at least 2 of these criteria
    - (i) Biochemical evidence of cholestasis based mainly on alkaline phosphatase elevation
    - (ii) Presence of anti-mitochondrial antibody (AMA)
    - (iii) Histologic evidence of nonsuppurative destructive cholangitis and destruction of interlobular bile ducts
  - Primary sclerosing cholangitis
  - Wilson's disease as defined by ceruloplasmin below the limits of normal and consistent liver histology
  - Alpha-1-antitrypsin(A1AT) deficiency as defined by diagnostic features in liver histology (confirmed by alpha-1 antitrypsin level less than normal; exclusion at the discretion of the study physician)
  - History of hemochromatosis or iron overload as defined by presence of 3+ or 4+ stainable iron on liver biopsy
  - Drug-induced liver disease as defined on the basis of typical exposure and history
  - Known bile duct obstruction

- Suspected or proven liver cancer
- Any other type of liver disease other than NASH
- Serum alanine aminotransferase (ALT) greater than 300 U/L
- Serum creatinine of 2.0 mg/dL or greater
- Unstable therapy for components of the metabolic syndrome (ie. recent starting or stopping of insulin sensitizing agent, lipid lowering agent, and/or antioxidant therapy). Recent starting or stopping (for more than 7 days) the use of a thiazolidinedione (pioglitazone or rosiglitazone) 90 days before the entry biopsy or anytime thereafter
- Use of any prescription or over-the-counter medication or herbal remedy that are believed to improve or treat NASH or liver disease or obesity for the 90 days prior to baseline liver biopsy or prior to randomization
  - Patients must not take any other agent to treat NASH except the treatment assigned after randomization.
- Inability to safely obtain a liver biopsy
- Active substance abuse including inhaled or injection drugs in the year prior to screening
- Pregnancy, planned pregnancy, potential for pregnancy and unwillingness to use effective birth control during the trial, breast feeding
- Any other condition which, in the opinion of the investigator, would impede compliance or hinder completion of the study
- A contraindication to MRI examinations
- Extreme claustrophobia
- Weight or girth exceeds the scanner capabilities
- Any condition or circumstance that, in the opinion of the site investigator, would interfere with completion of MR examinations
- Failure to give informed consent

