## 2.6. Summary

This study will advance several goals of the NIH Action Plan: 1) establish a multidisciplinary team to develop quantitative methodologies and imaging protocols for liver, 2) validate diagnostic criteria and methodologies for imaging in liver in both a cross-sectional and a longitudinal dietary intervention study of patients with NAFLD, 3) create a liver tissue bank with correlative imaging data, 4) develop reliable non-invasive MR markers to distinguish simple steatosis from NASH, and 5) define the *dynamic* changes in metabolism, energy homeostasis, and MR biomarkers as they relate to fructose-related liver injury.

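### The catch-all exclusion in section 8.3 names NASH where the rest of the plan admits NAFLD; applied literally, it would bar patients with simple steatosis

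*Combined protocol and SAP*

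**What the plan says.** Section 8.3 opens with the rule that "Patients who satisfy any of the following exclusion criteria will be ineligible for enrollment". One of its bullets is "Any other type of liver disease other than NASH". A separate 8.3 bullet, on other chronic liver diseases, carries an exemption: "with the exception of a prior diagnosis of NAFLD or NASH-related cirrhosis".

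Section 8.2 sets the NAFLD entry criteria more widely. It admits "Patients who have had a liver biopsy showing NAFLD within 6 months of the Screening visit", patients about to have a standard-of-care biopsy for NAFLD, and, in addition, "anyone with a prior diagnosis of NAFLD or NASH-related cirrhosis (histologically or clinically) may also enroll". None of these routes requires NASH. Section 8.1 says that "any patient with suspected NAFLD will be considered eligible if all inclusion and no exclusion criteria are met". Sections 3.1, 3.4 and 8.1 plan 30 healthy controls and 70 patients with NAFLD.

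Among the aims in section 2.6 is to "develop reliable non-invasive MR markers to distinguish simple steatosis from NASH".

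**The concern.** Section 2.1 presents NASH as the more serious form within NAFLD, and section 2.6 treats simple steatosis as distinct from it. A patient with steatosis but no steatohepatitis therefore has NAFLD, meets 8.2, and also meets the 8.3 bullet. Since one exclusion is enough, the exclusion prevails on a literal reading.

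Two things are at stake. The first is the case mix: with simple steatosis removed, the mild end of the histologic spectrum is missing from a study that relates MR and metabolic measures to histology. The second is consistency. Section 8.2 lets some patients in on a clinical diagnosis without a recent biopsy, and section 2.4 says that enzymes and conventional imaging cannot grade or stage the disease. For those patients NASH status may be unknown at screening. The bullet could then be enforced only where histology exists, and selection would depend on how a patient was diagnosed.

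**Working it through.** The plan states no figure that depends on this bullet, so the check is mainly a comparison of the texts.

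**Step 1: does the bullet reach simple steatosis?**
- Any single exclusion bars enrolment (8.3, opening line).
- The bullet bars liver disease other than NASH (8.3).
- NASH is a subset of NAFLD (2.1).
- So NAFLD without NASH is barred on the literal reading.

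**Step 2: does another passage rescue these patients?**
- The exemption in 8.3 is attached to the bullet on other chronic liver diseases, not to this one. It also covers only a prior diagnosis, so it does not reach a first diagnosis made on the study biopsy.
- Section 8.2 admits NAFLD, but an inclusion criterion does not override an exclusion.
- Section 8.1 makes eligibility conditional on no exclusion being met.
- Section 9.2 counts patients whose biopsies fail the entry criteria as screening failures, so histology can trigger the bullet.

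None of these resolves the contradiction.

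**Step 3: which analyses are affected on the literal reading?**

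| Purpose | Where | Effect |
|---|---|---|
| Simple steatosis versus NASH | 2.6 | 0 patients on one side; cannot be done |
| Association with, or prediction of, histologic severity | 1.2, 3.6, 10.2 | Possible within NASH; range cut at the mild end |
| Healthy volunteers versus NAFLD | 10.2 | Planned 30 versus 70 kept; the result would describe NASH, not NAFLD |

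**Step 4: screening load.** The 70 is an enrolment target, so excluded candidates would be replaced. If a share s of otherwise eligible candidates has NAFLD without NASH, the expected number needed is 70 / (1 − s). The documents give no value for s; the values below are assumptions.
- s = 0.10: 70 / 0.90 = 77.8, about 78
- s = 0.20: 70 / 0.80 = 87.5, about 88
- s = 0.40: 70 / 0.60 = 116.7, about 117
- s = 0.50: 70 / 0.50 = 140

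The zero in the first row of the table does not depend on s.

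**The case against.** The strongest reply is that nobody would read the bullet literally. It begins as a sweep-up, follows a list of competing liver diseases, and sits in a plan that defines its cohort as NAFLD throughout. The study is single-center and its own investigators recruit. This stands as a statement of probable intent: nothing in the documents suggests that the sponsor chose to exclude simple steatosis, so the point is an inconsistency and not a criticism of a design choice. It does not remove the contradiction, because eligibility is decided on the written criteria.

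Three stronger readings are tempting, and the documents do not support them.

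- *The trial loses the contrast it depends on.* Steatosis versus NASH appears in 2.6 as one of several goals that the study would advance. It is not named in the objectives (1.2), the specific aims (3.1), the outcome measures (3.6) or the analysis section (10.2). The analyses named in 10.2 could still be run.
- *A fraction of the 70 is lost.* Multiplying 70 by an assumed share of simple steatosis treats an enrolment target as a pool of candidates. Under 9.2 ineligible patients are screening failures, and they can be replaced.
- *Patients are routinely infused and then found ineligible.* The detailed sequence in 9.4 puts the biopsy after the infusion, although the section's opening paragraph is less clear on order. It concerns only patients without a biopsy in the preceding 6 months. The same timing question arises for any Day 0 biopsy that fails the entry criteria, so it is not specific to this bullet.

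**Conclusion.** The bullet is wrong as written: it contradicts 8.2, the planned NAFLD cohort and the exemption elsewhere in 8.3. If applied literally, it makes the 2.6 goal of separating simple steatosis from NASH unattainable, removes the mild end of the severity range used in 1.2, 3.6 and 10.2, and turns the NAFLD group into a NASH group. It does not reduce the planned 70, and it leaves severity within NASH analysable. The screening figures, about 78 to 140 candidates, rest wholly on an assumed 10% to 50% share.

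How far any of this happens depends on how the bullet is applied, which the documents do not say. The likely intent is a catch-all for competing diseases, so this is a low-priority correction, but a clear one.

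**What to change.** Reword the bullet so that it matches the population that 8.2 already admits, for example: *Any type of liver disease other than NAFLD (including NASH and NASH-related cirrhosis)*. Check 8.1, 8.2 and the exemption in 8.3 against the new wording so that all four name the same disease. If a NASH-only cohort was in fact intended, 8.2, 3.4 and the 2.6 goal would have to change instead.

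The cost is a few words in one bullet, with no added procedure, visit or analysis. The correction makes the steatosis-versus-NASH comparison possible but does not secure it: the plan sets no quota and no expected share for simple steatosis.

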## 9. Trial protocol—Study Visits and Events

### 9.1. Visit schedule overview

***Healthy controls*** will ONLY undergo:

- Screening for eligibility for enrollment (1-2 visits over a maximum of 8 weeks)
- Acute intravenous fructose challenge with measure of metabolism and energy homeostasis by magnetic resonance spectroscopy (MRS) (baseline and assessment of change over 60 minutes).
- MRI of the liver

Data collected from healthy controls will be used as reference and optimization values for which study will assess metabolic and energy homeostatic measures in those with NAFLD.

***Patients with NAFLD*** will undergo the following related activities study phases:

- Screening for eligibility for enrollment (1-2 visits over a maximum of 8 weeks)
- Acute intravenous fructose challenge with measure of metabolism and energy homeostasis by magnetic resonance spectroscopy (MRS) (baseline and assessment of change over 60 minutes. MRI of the liver

- Co-localization of non-invasive MR biomarkers with liver biopsy procedure.

## 9.2. Screening and Baseline Data Collection

Patients who appear to be eligible after chart review and have completed of standard of care tests and procedures for NAFLD or suspected NAFLD will be invited to undergo screening. Recording of screening data may not start until the patient has signed the consent statement. Screening and baseline data collection procedures will include questionnaires, physical examination, measurement of fasting serum glucose and insulin, routine liver, lipid and metabolic tests, uric acid and urine analysis for pregnancy testing. Standard therapy for NAFLD will be reviewed. Risks, potential benefits and alternatives to study participation will be reviewed in detail.

Patients suspected of having NAFLD, requiring a standard of care biopsy to establish their diagnosis and guide their clinical management, will be approached to participate in this study. Patients with a historical biopsy confirming NAFLD within 6 months of the Screening visit will also be approached to participate in this study.

All participants who sign the consent statement will be registered in the trial database. Patient charts will be reviewed for historical information. Each participant who starts screening will be accounted for at the end of screening, as either screening success (enrolling in the trial) or a screening failure. A screening failure is defined as a participant who signed the consent form, but is found to be ineligible prior to randomization; patients who meet medical eligibility criteria but who refuse enrollment in the trial; and patients whose liver biopsies do not meet entry criteria. Reasons for screening failure will be recorded in the trial database.

The patient will sign the consent at screening visit to obtain any tests and procedures needed to finalize eligibility after chart review and will undergo a history and physical examination to identify other abnormalities and contraindications for participation. Anthropomorphic assessments (body weight [kg], body height [m], body mass index [BMI], waist circumference [cm], hip circumference [cm] and waist-to-hip ratio; vital signs (systolic and diastolic blood pressure, heart rate, respiratory rate, body temperature); and general physical findings, including hepatosplenomegaly, peripheral manifestations of liver disease, ascites, wasting or fetor, will be collected and recorded. Use of anti-NASH, antidiabetic, statin and fibrate medications in the 90 days prior to the biopsy will be obtained and recorded. Laboratory test results that need to be recorded from chart review or obtained as part of screening visit 1 include hepatitis B (HBsAg) and hepatitis C (anti-HCV), antinuclear antibody (ANA), anti-smooth muscle antibody (ASMA), anti-mitochondrial antibody (AMA), ceruloplasmin (if patient is less than 40 years old), A1AT concentration, iron and transferrin saturation, immunoglobulins (IgA, IgG, IGM), fasting glucose, insulin, and free fatty acids; CBC (Hgb, WBC, platelets, MCV, hematocrit), prothrombin time and INR, complete metabolic panel (sodium, potassium, chloride, bicarbonate, calcium, phosphate, BUN, creatinine, uric acid, albumin, total protein), GGT and hepatic panel (ALT, AST, alkaline phosphatase, total bilirubin, direct bilirubin), fasting lipid profile (total cholesterol, triglyceride, LDL, HDL), and hemoglobin A1c (HbA1c). Frequency and amount of alcohol intake will be obtained. Women of childbearing potential must have a negative pregnancy test.

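### Every participant receives a rapid intravenous fructose bolus, but neither the exclusion criteria nor the screening history asks about disorders of fructose metabolism (a low-likelihood safety gap)

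*Combined protocol and SAP*

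**What the plan says.** Section 5 applies the fructose challenge to all subjects: after an overnight fast, 250 mg/kg in 25 to 50 mL of saline, given through the venous catheter over 30-60 seconds. Section 9.1 lists the challenge for healthy controls as well as for patients with NAFLD. Section 3.4 sets the numbers at 30 controls and 70 patients.

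Section 8.3 contains one exclusion tied to each of the other two procedures: "A contraindication to MRI examinations" and "Inability to safely obtain a liver biopsy". It names no condition that would make the fructose bolus unsafe. Two general exclusions come nearest: "Any other type of liver disease other than NASH" and "Any other condition which, in the opinion of the investigator, would impede compliance or hinder completion of the study".

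At screening, section 9.2 says the participant "will undergo a history and physical examination to identify other abnormalities and contraindications for participation". The laboratory list that follows is long, but it has no item bearing on fructose handling, and no question on fructose or sugar intolerance is specified.

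A control enters under section 8.2 as "Healthy control as defined by normal liver aminotransferases AND no evidence of NAFLD on radiologic imaging studies", with a clear historical biopsy as the alternative to imaging.

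Section 11.2.1 describes what fructose does in general (more lactate and uric acid, depletion of high-energy phosphate, inhibited protein synthesis) and names one hazard, a theoretical lactic acidosis in hepatic disease. It does not mention disorders of fructose metabolism.

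**The concern.** The bolus is the agent under study and is given to everyone, yet it is the one study procedure without its own eligibility check. Once injected it cannot be taken back, so screening is the point at which the written plan can prevent an unsafe exposure.

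The person at risk is someone with an inherited disorder of fructose metabolism, such as hereditary fructose intolerance, which has not been diagnosed or is not volunteered. That a rapid intravenous load could seriously harm such a person is general clinical knowledge. The protocol does not say so, and section 11.2.1 supports it only in part, through the general effects it lists. Controls deserve particular thought, because section 9.1 says their data serve as reference and optimisation values.

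What is at stake is participant safety. Nothing here affects the estimates, the tests or the power.

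**Working it through.** **Does any existing provision reach an unrecognised case?** The plan gives no figure on this point, so the first check is of the text.

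| Provision | Section | Reaches an unrecognised case? |
|---|---|---|
| History and physical examination for contraindications | 9.2 | Only if the examiner happens to ask; nothing about fructose is prompted |
| Laboratory list | 9.2 | No; no item on fructose handling |
| Exclusion of liver disease other than NASH | 8.3 | No; it needs a recognised liver disease |
| Investigator's discretion | 8.3 | No; it needs a recognised condition and is worded around compliance and completion |
| Liver-function, ALT and creatinine limits | 8.3 | Not if the values are normal |
| Dietary recall (ASA24) and food-frequency questionnaire (DHQ) | 6.3, 6.4 | No; they measure intake and are not tied to eligibility |

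A control with normal aminotransferases and imaging and an unrecognised disorder therefore meets sections 8.2 and 8.3 as written and would be dosed.

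**How likely is this?** The number exposed is 30 + 70 = 100 (section 3.4). The documents give no frequency for these disorders, so every rate below is an assumption.

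1. Any case among 100, as 1 − (1 − p)^100, with p assumed between 1/50,000 and 1/10,000:
   - p = 1/50,000: 0.20%; expected number 100/50,000 = 0.002.
   - p = 1/10,000: 0.995%; expected number 100/10,000 = 0.010.
   - At a lower p of 1/100,000 the chance is 0.10%.
2. Unrecognised cases, if 25% to 75% of cases are unrecognised (assumed):
   - Expected number: 0.002 × 0.25 = 0.0005 to 0.010 × 0.75 = 0.0075.
   - Chance of at least one: 1 − (1 − 0.25/50,000)^100 = 0.050% to 1 − (1 − 0.75/10,000)^100 = 0.747%.
3. Effect of a history question that catches 50% to 90% of these (assumed, since it relies on self-report):
   - Expected number left: 0.0005 × 0.10 = 0.00005 to 0.0075 × 0.50 = 0.00375.
   - Expected number averted: 0.0005 × 0.50 = 0.00025 to 0.0075 × 0.90 = 0.00675.

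**What would the question cost in participants?** If 1% to 10% answer yes (assumed), 1 to 10 of 100 need physician review. If 5% to 20% of those remain suspected (assumed), between 1 × 0.05 = 0.05 and 10 × 0.20 = 2 are turned away. Excluding on every positive answer would lose 1 to 10.

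**Size of the dose.** At assumed weights, 0.25 g/kg × 70 kg = 17.5 g and 0.25 g/kg × 100 kg = 25 g, delivered within a minute.

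**The case against.** The strongest reply is that the harm comes from outside the documents and that the yield is close to nil. No section mentions an inherited disorder of fructose metabolism, and section 11.2.1 opens by noting that fructose has been recommended as an intravenous energy source, including in hepatic disease. Every rate above is assumed, and the question would avert at most 0.00675 exposures in the whole trial. Several layers already stand: chart review, a discussion of risks at screening (both section 9.2), recruitment through liver clinics by the investigators (section 8.1), the liver-function limits, and a physician's history that need not be scripted in a protocol. An exclusion for known or suspected disease does little by itself for a case nobody has recognised.

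Much of this stands. The likelihood is very low, the harm has to be labelled as general clinical knowledge, and the computed ranges hold only within the assumed frequencies. It is also true that the history question, not the exclusion line, does most of the work on the remaining gap. Nothing is claimed about the consent form, which was not available; a warning there would not be an eligibility criterion in any case.

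What does not stand is that the gap is already closed. Each existing layer stops only recognised cases or has no bearing on eligibility. Nor is it foreign to this protocol to name individual disorders: section 8.3 lists Wilson's disease and alpha-1-antitrypsin deficiency, and section 9.2 orders ceruloplasmin (under age 40) and alpha-1-antitrypsin concentration. Those items may serve diagnostic purity, but they show that this level of detail is normal here.

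**Conclusion.** The concern holds. Everyone receives the bolus, section 8.3 has no exclusion for a disorder of fructose metabolism, and the screening history is generic. On the stated assumptions the chance of an unrecognised case among 100 participants is about 0.05% to 0.75%, so an event is very unlikely. The case for change rests on a possibly serious and irreversible exposure set against a very small cost. It is a worthwhile improvement to participant safety, not a fault that undermines the trial, and it has no bearing on the statistical analysis. The omission can be read directly from the text; the frequency and the severity of harm cannot.

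**What to change.** - **Section 9.2:** ask every participant, controls included, about lifelong avoidance of fruit or sweet foods, systemic illness after eating them, and any family history. Have the study physician review each positive answer before dosing, so that simple digestive intolerance does not exclude automatically.
- **Section 8.3:** add an exclusion for a known or suspected inherited disorder of fructose metabolism, for example hereditary fructose intolerance.

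The cost is one question at a visit already planned, one line of text, and the handful of physician reviews estimated above. The downside is an occasional participant turned away on history alone. Because the question depends on self-report, it reduces the gap without closing it.
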